5.7 Handling of Missing Data

This study relies primarily on clinical endpoints, with constant monitoring of the subjects by the quarantine unit clinical staff. The likelihood of missing data for the primary and secondary endpoints is therefore low. However, in the event a significant amount of data is missing, a full investigation will need to be performed to carefully evaluate the study conduct. Participants who did not receive the challenge virus will not be included in any of the analyses, however data will be included in safety listings (i.e. AE, Concomitant Medication, Laboratory, etc.). All participants who received at least one FLU-v vaccination will be included in the SAF population.

For all endpoints where missing data occurs (as defined in section 5) the following sequence of analyses will be performed in order to understand the impact of the missing data on the results.

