A randomized, double-blind, placebo-controlled efficacy and safety trial of FLU-v administered as 2 vaccinations or 1 vaccination vs placebo prior to intranasal challenge with the Influenza A 2009 H1N1 human virus.

In this study, the main efficacy comparisons are for each of the FLU-v groups to placebo. The study will not compare the two FLU-v dosing arms as the study may not have enough power to detect a significant difference in the primary efficacy endpoint of mild to moderate influenza induced disease (MMID) rates between the FLU-v groups.

2 Current Approved Study Protocol

The current approved study protocol is version 3.0 dated 18APR2017.

3 Study Hypothesis

The hypothesis is that vaccination with one dose or two doses of FLU-v + adjuvant will significantly reduce MMID when compared to individuals vaccinated with placebo.

4 Sample Size Justification and Analysis Plan

Sample size was calculated for 3 groups, a placebo group and 2 Investigational Medicinal Product (IMP) (i.e. one dose and two doses of FLU-v) groups. Each FLU-v arm will be compared to the placebo arm. Groups are randomized 1:1:1. All comparisons are at the 0.05 one-sided alpha level, and any p-value less than 0.05 would be considered as significant. This may increase the type-I error rate of potentially moving forward with an inactive treatment, but is appropriate for an early phase II trial of this type. Sample sizes assuming two different placebo MMID rates and for 80% power are given in Table 1 below.

Table 1.

Probability (rate) of MMID		Sample size per arm	Total sample size	Power	One-sided alpha
Placebo	Vaccine				
0.7	0.4	40	120	80%	0.05
0.8	0.5	37	111	80%	0.05

Table 1 shows that a sample size of 120 (40 per group) provides good power (80%) for a placebo MMID rate of 0.7 and an absolute reduction of 30%. The difference is clinically meaningful and the assumptions of a placebo MMID rate of 0.70 is reasonable and based on past experience.¹

5 Analysis Plan and Reports

The primary analysis population will be the Intent to Treat (ITT) population and will be used for the analysis of all primary and secondary endpoints. The ITT will include those participants who received both vaccination and challenge with an influenza virus.

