The Per Protocol (PP) analysis population is defined as a subset of the ITT population who have no major protocol deviations (complied with the protocol appropriately in order to ensure that these data would be likely to reveal the effect of treatment). At a Blinded Data Review Meeting (BDRM), which will take place prior to database lock, ITT analysis set subjects will be reviewed for their inclusion/exclusion to the PP population.

Any participant who received at least one immunization but did not receive the influenza challenge virus will not be part of the ITT or PP analysis populations, but will be part of the safety population (SAF).

Subject disposition will be presented as a flow chart and will include number of subjects randomised, number of subjects that received one or two doses of FLU-v or placebo, number of vaccinated subjects that received the challenge virus, the number of subjects that withdrew from the study and the number of subjects that completed the study in each arm. Primary, secondary and safety endpoints will be presented in the clinical study report. Analysis and reporting of exploratory endpoints may be separate to the clinical study report.

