14.2.2.7*	Total Number of Symptoms Experienced – Intent to Treat
14.2.2.8*	Peak Total number of Symptoms – Intent to Treat
14.2.2.9*	Symptom Severity Score (FLUPRO) – Intent to Treat
14.2.2.10*	Proportion of Asymptomatic Infected Subjects – Intent to Treat
14.2.2.11.1	Summary of Adverse Events from the Post-Vaccination Diary Card (Days -43 to -23) – Intent to Treat
14.2.2.11.2	Summary of Adverse Events from the Post-Vaccination Diary Card (Days -22 to -2) – Intent to Treat
14.3.1.1	Treatment Emergent Adverse Events Analysis – Safety
14.3.1.2	Treatment Emergent Adverse Events Summary (Overall) – Safety
14.3.1.3	Treatment Emergent Adverse Events Summary (Pre-inoculation) – Safety
14.3.1.4	Treatment Emergent Adverse Events Summary (Post-inoculation) – Safety
14.3.2.1.1	Treatment Emergent Adverse Events by Classification (Pre-inoculation – Safety
14.3.2.1.2	Treatment Emergent Adverse Events by Classification (Post-inoculation) – Safety
14.3.2.2.1	Treatment Emergent Adverse Events reported as Mild in Intensity by Classification (Pre-inoculation) – Safety
14.3.2.2.2	Treatment Emergent Adverse Events reported as Mild in Intensity by Classification (Post-inoculation) – Safety
14.3.2.3.1	Treatment Emergent Adverse Events reported as Moderate in Intensity by Classification (Pre-inoculation) – Safety
14.3.2.3.2	Treatment Emergent Adverse Events reported as Moderate in Intensity by Classification (Post-inoculation) – Safety
14.3.2.4.1	Treatment Emergent Adverse Events reported as Severe in Intensity by Classification (Pre-inoculation) – Safety
14.3.2.4.2	Treatment Emergent Adverse Events reported as Severe in Intensity by Classification (Post-inoculation) – Safety
14.3.2.5.1	Treatment Emergent Adverse Events Reported as Related to Vaccine by Classification (Pre-inoculation) – Safety

Table	Title
14.3.2.5.2	Treatment Emergent Adverse Events Reported as Related to Vaccine by Classification (Post-inoculation) – Safety
14.3.2.6	Treatment Emergent Adverse Events Related to Inoculation by Classification (Post-inoculation) – Safety
14.3.3	Clinical Laboratory Safety - Overall Summary

*Per Protocol (PP) population differs from Intent to Treat (ITT) by only 1 subject. The data will be presented for Intent to Treat only in the final analyses, unless analyses of using PP differs significantly. If PP is presented, an additional digit will be added to table numbers with ITT as 14.2.X.X.1 and PP as 14.2.X.X.2.

Summary of Figures

For all figures listed below:

[figure not shown]

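### SAP 5.7 conflicts with SAP 5 and 5.6 on who is analysed for safety, and the diary-card tables count only subjects who reached challenge

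*SAP*

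**What the plan says.** **Safety population.** SAP section 5 deals with "Any participant who received at least one immunization but did not receive the influenza challenge virus": such a subject is outside ITT and PP "but will be part of the safety population (SAF"). The rule names no arm. SAP 5.7 says: "Participants who did not receive the challenge virus will not be included in any of the analyses, however data will be included in safety listings". Its next sentence reads: "All participants who received at least one FLU-v vaccination will be included in the SAF population". No section gives one complete definition of the safety population for all three arms.

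**Comparisons that need placebo.** SAP 5.6 plans Fisher's exact tests of adverse-event rates against placebo, and a laboratory presentation by treatment group and placebo.

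**Table assignments.** In the SAP section 8 list of tables, the treatment-emergent adverse event tables, including "Treatment Emergent Adverse Events Summary (Post-inoculation"), are on the safety population. The two diary-card tables, the first titled "Summary of Adverse Events from the Post-Vaccination Diary Card (Days -43 to -23"), are on ITT. SAP section 5 defines that set: "The ITT will include those participants who received both vaccination and challenge with an influenza virus".

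**Diary events and adverse events.** Vaccine-related adverse events from the 21-day diary cards are a secondary endpoint (protocol 6.2.1). Under protocol 15.2.2, diary symptoms do not become individual adverse events unless judged clinically significant.

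**The concern.** There are two faults. First, a programmer cannot follow section 5 and 5.7 together. A subject who received FLU-v and left before challenge is in the safety population under section 5 and under the second sentence of 5.7, but in no analysis under the sentence before it. A placebo recipient who left before challenge is in the safety population under section 5 and unmentioned in 5.7.

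Second, the diary tables describe reactions from Day -43 to Day -2 but count only subjects who were inoculated on Day 0. Inclusion therefore depends on something that happens after the exposure and may be caused by it. Protocol 7.4.2 lists clinically significant laboratory findings and a severe systemic allergic reaction among the reasons for stopping participation. Subjects who leave before challenge are replaced (protocol 7.4.1 and 7.5), so the ITT denominator can still reach 123 and the loss does not show in the table.

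Tolerability is the stated safety objective (protocol 6.4), and safety is part of choosing the FLU-v regimen for Part B (protocol 5.3). If reactions make subjects more likely to leave, the diary tables understate reactogenicity.

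**Working it through.** **Passages side by side**

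| Subject | SAP 5 | SAP 5.7 | Tables as assigned in SAP 8 |
|---|---|---|---|
| FLU-v, challenged | ITT | Safety population | Diary and adverse-event tables |
| Placebo, challenged | ITT | Not mentioned | Diary tables; adverse-event tables only if in the safety population, as 5.6 requires |
| FLU-v, not challenged | Safety population | Safety population, yet in no analysis | Not in diary tables; adverse-event tables under section 5 only |
| Placebo, not challenged | Safety population | In no analysis | Not in diary tables; adverse-event tables under section 5 only |

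The last two rows conflict between sections. Their absence from the diary tables does not depend on how 5.7 is read, because it follows from the ITT definition alone.

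**How many subjects.** The plan gives no number vaccinated but unchallenged, so there is no figure to reproduce. The sample size is not affected. Inputs:

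- Number challenged: up to 123 (protocol synopsis and 7.1).
- Loss before challenge: an assumption. In the earlier challenge study 32 subjects were vaccinated and 28 quarantined (protocol 5.2.3.1), a loss of 4/32 = 12.5%. I take 5% and 20% as the range around it.

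Vaccinated = 123 / (1 − loss), rounded up:

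- 5%: 123 / 0.95 = 129.5, so 130 vaccinated and 7 missing.
- 12.5%: 123 / 0.875 = 140.6, so 141 vaccinated and 18 missing (6 per arm if spread evenly).
- 20%: 123 / 0.80 = 153.75, so 154 vaccinated and 31 missing.

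**What the omission can do to a rate.** Suppose a diary reaction has true frequency p = 10%, a share q of those who have it leave before challenge, and 5% of the others leave. The ITT table then shows, in expectation, p(1 − q) / [p(1 − q) + (1 − p)(0.95)]:

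- q = 5%: 0.095 / 0.950 = 10.0%
- q = 25%: 0.075 / 0.930 = 8.1%
- q = 50%: 0.050 / 0.905 = 5.5%
- q = 75%: 0.025 / 0.880 = 2.8%

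There is no bias when loss is unrelated to the reaction, and understatement when it is related. All values of p and q are hypothetical.

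**Post-inoculation denominators.** If the safety population includes unchallenged subjects, as section 5 says, and its full size is the denominator, a post-inoculation rate is multiplied by 123/130 = 0.95, 123/141 = 0.87 or 123/154 = 0.80. The SAP text does not state which denominator these tables use.

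**The case against.** **A reader might infer that 5.7 removes the placebo arm from the safety population.** The documents do not support this. The sentence says who is included and does not say only. Section 5 admits any immunised subject without naming an arm, 5.6 plans comparisons with placebo, and challenged placebo subjects are in the ITT diary tables. What stands is that the sentence is incomplete.

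**A reader might infer that early leavers vanish from safety.** They do not. Under section 5 they are in the safety population and so in the treatment-emergent tables, including the severe and vaccine-related pre-inoculation tables. SAP 5.6 summarises adverse events leading to withdrawal, and there is a diary-card listing (16.2.5.3). Since 5.7 concerns missing data for the primary and secondary endpoints, its exclusion was probably meant for efficacy. But it does not say so, and ordinary diary reactions in early leavers would appear only in the listing.

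**A reader might picture several severe reactions in one arm disappearing from view.** That sits badly with protocol 18.4.1, under which the study is terminated if two or more subjects have severe or clinically significant adverse events at least possibly related to FLU-v (the synopsis adds the same organ class). The realistic exposure is to reactions below that level.

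**The ITT label follows a rule.** SAP section 5 assigns ITT to all primary and secondary endpoints, and the diary-card endpoint is secondary. That explains the choice but does not make a challenge-dependent set suitable for a pre-challenge endpoint.

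**Losses may be unrelated to the vaccine.** Illness, fever, influenza contact or the admission virus screen can also prevent challenge. No reasons are given for the 4 of 32, and that study injected 1 mL into the forearm, where this one injects 0.5 mL into the upper arm. This is fair, and it is why the size is given as a range and bias is called possible.

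**Post-inoculation dilution and exclusion under 5.7 cannot both occur,** since they need opposite readings of 5.7. The table shells are a separate document and may state the denominator. This part is a request for clarity only.

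**Conclusion.** The point holds in two parts. SAP 5.7 contradicts section 5 on whether unchallenged subjects are analysed, and its safety-population sentence is incomplete beside the placebo comparisons in 5.6. Independently of that wording, both diary-card tables are conditioned on reaching challenge, and the adverse-event tables do not make up the difference because of protocol 15.2.2.

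About 7 to 31 vaccinated subjects would be absent from the diary tables, on an assumed loss of 5% to 20% before challenge; 18 of 141 corresponds to the earlier study's loss. Whether their absence biases the reaction rates depends on why they left, which the documents do not say. If leaving is related to reactions, the bias is towards better tolerability. The evidence does not show that the placebo comparator is lost, or that early leavers drop out of all safety reporting.

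**What to change.** 1. Define the safety population once, in SAP section 5: all subjects given at least one injection of FLU-v or placebo, whether or not challenged, analysed as treated. Replace the FLU-v-only sentence in 5.7 with a reference to it.
2. Limit the 5.7 exclusion of unchallenged subjects to the efficacy analyses. Keep the commitment to list their safety data; deleting the sentence outright would lose it.
3. Move tables 14.2.2.11.1 and 14.2.2.11.2 to the safety population, with recipients of the first and of the second injection as the respective denominators. Add this as a stated exception to the rule that secondary endpoints use ITT.
4. State that post-inoculation adverse-event tables use inoculated subjects as denominator, and check the shells against this.
5. Report by arm the number vaccinated but not challenged, with reasons, so that the assumed range can be replaced by the actual count.

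Items 1 to 4 cost SAP wording and table headers. Item 5 uses disposition data already collected. No new data are needed and the sample size is unchanged.

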5.7.1 Primary endpoint

- Primary analysis: impute the placebo group's proportion of events for the missing data in each group.
- Sensitivity analysis: ignore missing data.
- Sensitivity analysis: for placebo group impute observed proportion from vaccine group and for vaccine group impute observed proportion from placebo group.

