9.3.2 Virus Inoculation (Day 0)

All baseline procedures and tests will be performed prior to challenge virus administration. Once it has been determined that the participant still meets eligibility criteria for the study and that he/she is comfortable in the unit, administration of the challenge virus will proceed at a dose of 10^7 TCID₅₀ on Day 0. Once the influenza challenge virus has been administered, participants will remain hospitalized in isolation on the unit for a minimum of 8 additional days and will be discharged only after they meet the discharge criteria described below.

9.3.3 Day 1 through 7

While admitted to the Quarantine Unit, participants will remain in isolation in their room. Participants will undergo study procedures which will be conducted as detailed on the Time and Events table 9.2

Participants will be discharged when they meet the following discharge criteria: 2 consecutive negative morning nasal swabs (that occur on 2 different but consecutive days) for influenza A, are afebrile, show no signs of significant influenza symptoms, and are clinically and hemodynamically stable. It is expected that participants will shed virus for 3 to 5 days post inoculation; therefore, we expect most participants to have 2 consecutive negative nasopharyngeal swabs by Day 7 of the study.

The FLU-PRO questionnaires will be completed in paper form.

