16.2 Sample size

The primary objective of this study is to examine whether there is a difference in the MMID rates post inoculation between either of the 2 FLU-v arms and placebo. A sample size of 41 subjects per arm (total 123) will provide 80% power to detect a difference in MMID rates of .70 versus .40 using a one sided 0.05 significance level. The table below shows the power that the study would have with 41 patients per arm for other MMID rates. The sample size calculations do not adjust for multiple comparisons.

Table 1. Power with 41 subjects per arm with various MMID probabilities

Probability of MMID in placebo	Probability of MMID in Vaccinated arms	Power
.70	.40	.80
.70	.44	.70
.70	.47	.60
.60	.30	.80
.60	.34	.70
.60	.37	.59
.50	.21	.81
.50	.25	.68
.50	.28	.56

In this study the main comparisons are for each of the FLU-v dose groups to placebo. The study will also compare the FLU-v dosing arms but the study will not have adequate power to detect a significant difference in MMID rates at the predicted treatment rates. This study does not control for multiple comparisons since we are trying to maintain a small sample size but yet have high power to detect the pre-defined primary objective of efficacy versus placebo when FLU-v is truly beneficial. All comparisons will be made at the one sided 0.05 significance level.

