5.2 Primary Endpoint: Incidence of MMID

MMID is defined as positive if a participant has both detectable shedding, as evaluated by RT-qPCR (reverse transcriptase quantitative polymerase chain reaction), and at least one symptom,

as observed on the Physician Assessment of Influenza Symptoms (PAI), at any time during subject quarantine, starting from the evening of Day 1 post-inoculation through the expected end of the quarantine period, Day 7, Discharge. The analysis of this endpoint will be performed by comparing the MMID rates in each of the FLU-v groups to the placebo group. Comparisons will be performed using one-sided Fisher's exact test, and the proportion of subjects with MMID and corresponding p-value will be presented. If a subject has no nasal swab data on two consecutive days, and the available recorded data shows no shedding, the MMID for that subject will be considered as missing. Similarly, if symptom data is not recorded on two consecutive days, and the available recorded data shows no symptoms, the MMID will be considered as missing for that subject. However, if a subject is positive for viral shedding and experiences at least one symptom with the available recorded data, that subject will be included in the MMID analysis. The primary analysis will incorporate missing data as described in section 5.7. The statistical summary data will be presented as tables and figures as described in sections 8-9 of this document.

5.3 Secondary Objectives:

To determine the overall effect of FLU-v on influenza disease based on disease severity measures (presence or absence of symptoms or shedding, symptom severity, symptom and shedding duration, total symptoms and shedding, and peak symptom and shedding). Viral shedding was evaluated by RT-qPCR and symptoms were evaluated by PAI, from the evening of Day 1 post-inoculation (more than 24 hours after inoculation) through the expected end of the quarantine period (Day 7, Discharge).

5.4 Secondary Endpoints:

- Overview of symptoms (PAI) and of viral shedding (RT-qPCR) from the evening of Day 1 post-inoculation (more than 24 hours after inoculation) through Day 7.

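### MMID can be missing only when the recorded swabs or symptoms are all negative, yet the primary analysis imputes the placebo group's unconditional rate, even for subjects who cannot be cases, and gives no rule for turning it into whole counts

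*SAP*

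**What the plan says.** MMID needs two components between the evening of Day 1 and Day 7: shedding by RT-qPCR and at least one symptom on the physician assessment (SAP 5.2). On the test, SAP 5.2 states: "Comparisons will be performed using one-sided Fisher's exact test". On the level, SAP section 4 states: "All comparisons are at the 0.05 one-sided alpha level".

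SAP 5.2 has two routes to a missing outcome. For a subject without swabs on two consecutive days, the rule ends: "and the available recorded data shows no shedding, the MMID for that subject will be considered as missing". The same applies to a two-day gap in symptom data with no symptom recorded. A subject with a gap but with recorded shedding and a symptom stays in the analysis.

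SAP 5.7.1 sets the primary handling: impute the placebo group's "proportion of events for the missing data in each group". There are two sensitivity analyses. One ignores missing outcomes. The other swaps the observed proportions between placebo and vaccine. SAP 5.7.3 uses the same two imputations as sensitivity analyses for the secondary binary endpoints. SAP 5.7 expects little missing data and gives no number.

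**The concern.** The 5.2 rule selects missing subjects for having looked negative on the days that were recorded. The rate imputed in 5.7.1 is the chance of MMID over the whole window for a placebo subject about whom nothing is known. The subject's own negative days are not used.

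The clearest error needs no assumption. A subject with complete, symptom-free physician assessments and a two-day swab gap cannot have MMID, whatever the lost swabs would have shown. A subject with complete negative swabs and a symptom gap cannot have it either. SAP 5.2 calls both missing, and 5.7.1 gives each about 0.7 of a case in expectation.

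Fisher's exact test also needs whole counts, while 5.7.1 supplies a proportion. Rounding, a random draw and multiple imputation all fit the wording and can give different p-values. This is the primary analysis of a trial with about 41 subjects per arm, so one subject can matter in a borderline result.

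**Working it through.** **Inputs.** 41 per arm and MMID rates of 0.70 and 0.40 (Protocol 16.2); one-sided 0.05 (SAP section 4); one-sided Fisher's exact test (SAP 5.2). The number of missing outcomes is my assumption, because the documents give none.

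**The plan's own figure.** Protocol 16.2 says that 41 per arm "will provide 80% power to detect a difference in MMID rates of .70 versus .40 using a one sided 0.05 significance level". Exact enumeration of the one-sided Fisher test gives 81.3%. At the SAP's 40 per arm it gives 79.8%. Both agree with the stated 80%.

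**Is 0.70 too high?** Let h be the chance that a true case looks negative on the recorded days. Treating every non-case as looking negative,

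P(MMID | looks negative) = 0.70h / (0.70h + 0.30).

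- h = 0.05: 0.035/0.335 = 0.10
- h = 0.10: 0.070/0.370 = 0.19
- h = 0.30: 0.210/0.510 = 0.41
- h = 1: 0.70

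The answer stays below 0.70 whenever a case is less likely than a non-case to look negative.

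For swab gaps there is a guide to h. Protocol 9.3.3 says: "It is expected that participants will shed virus for 3 to 5 days post inoculation". An unbroken run of 3 to 5 days inside Days 1 to 7 cannot be hidden by a gap of exactly two days, so h = 0. A run of one or two days would be hidden with chance 12/42 = 0.286 or 6/36 = 0.167, averaging over all positions of run and gap. For symptom gaps the documents give no expected duration.

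**One missing placebo non-case.** Suppose the truth is placebo 28/41 and FLU-v 20/41.

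| Handling | Table | One-sided p |
|---|---|---|
| Counted as non-case | 28/41 v 20/41 | 0.058 |
| Dropped (complete-case) | 28/40 v 20/41 | 0.043 |
| Imputed 28/40 = 0.70, rounded to 1 | 29/41 v 20/41 | 0.035 |
| Swap: imputed 20/41 = 0.49, as 0 or 1 | 28/41 or 29/41 v 20/41 | 0.058 or 0.035 |

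Of the full fall in p of 0.058 − 0.035 = 0.023, dropping the subject already accounts for 0.058 − 0.043 = 0.015. Most of the shift therefore comes from the 5.2 definition.

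**Operating characteristics.** Assume that all missing subjects are true non-cases, and raise the rate among observed subjects so that the whole arm of 41 keeps its rate (for four missing at 0.70: 0.70 × 41/37 = 0.776). Imputed counts are rounded to nearest.

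| Missing | Measure | As non-cases | Dropped | Imputed |
|---|---|---|---|---|
| 2 placebo only | type I error, both arms 0.70 | 0.026 | 0.062 | 0.079 |
| 4 placebo only | type I error, both arms 0.70 | 0.021 | 0.129 | 0.132 |
| 4 FLU-v only | power, 0.70 v 0.40 | 81.8% | 66.9% | 59.4% |
| 2 in each arm | power, 0.70 v 0.40 | 82.2% | 83.3% | 82.7% |
| 4 in each arm | power, 0.70 v 0.40 | 83.3% | 88.1% | 84.5% |

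**Conversion to counts.**

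- Placebo 28/41; FLU-v 18 cases among 39 observed, two missing. Imputed: 2 × 28/41 = 1.37. As one case, 28 v 19 of 41, p = 0.037. As two, 28 v 20, p = 0.058.
- Placebo 29/41; FLU-v 20 among 40 observed, one missing. Imputed: 29/41 = 0.71. As none, 29 v 20, p = 0.035. As one, 29 v 21, p = 0.056.

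At the design rates, rounding up and rounding down disagree on significance in about 6% of trials with one missing subject in one arm. With one missing in each arm, both rounded the same way, the figure is about 0.1%.

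**The case against.** The best defence is that missing data should be rare, because subjects are in quarantine under constant observation, and that giving vaccinated subjects the placebo rate is a cautious choice. With few and balanced missing outcomes the primary result barely moves, as the equal-missingness rows show. That stands. The caution, however, holds only in the FLU-v arms. In placebo the same rule adds control cases and favours the vaccine.

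The swap analysis gives placebo the vaccine rate, which is less favourable to FLU-v when that rate is lower. It is a partial check, but it still imputes unconditional rates and has the same rounding gap.

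Three stronger readings are tempting, and the documents do not support them.

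- A reader might infer that the primary p-value cannot be computed. The SAP leaves the step from proportion to counts unstated; rounding, a draw or multiple imputation would all supply whole counts.
- A reader might infer that the true chance of MMID is near zero for every missing subject. Two days is a minimum gap, and subjects can withdraw from quarantine, which leaves longer ones. The 3-to-5-day expectation is general, FLU-v might shorten shedding, and the figure says nothing about symptom gaps. With most days lost, the placebo rate need not be too high for a placebo subject.
- A reader might blame imputation alone for a false success such as p = 0.035. Dropping the subject already gives p = 0.043.

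**Conclusion.** The point holds and should be corrected, but it does not undermine the design. A stated rule gives a wrong result for subjects with one component complete and negative: they are known non-cases but are treated as missing and imputed at about 0.7 of a case. For other missing subjects the imputed rate is generally too high, by an amount that depends on gap length and on a symptom duration that the documents do not give.

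The direction of bias depends on the arm. The effect is small when missing outcomes are few and balanced, and material when they fall in one arm. The type I error and power figures assume two or four missing true non-cases per affected arm; they illustrate the rule and do not forecast this trial. Neither sensitivity analysis counts such subjects as non-cases, and complete-case carries a similar bias. The missing conversion rule is a separate, smaller gap, which matters only in borderline tables.

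**What to change.** 1. **SAP 5.2.** Classify MMID as a non-case, not missing, when either component is fully observed and negative. Define fully observed; the section's own tolerance of gaps shorter than two consecutive days would serve.
2. **SAP 5.7.1.** Before unblinding, state one whole-count rule for the remaining unresolved subjects that uses their observed negative days. For example, count as non-cases those whose only gap is two swab days, citing the 3-to-5-day expectation as the assumption. For the rest, draw 0/1 outcomes with a fixed seed and a stated way of combining p-values.
3. **Bound.** Add one worst-case analysis in whole counts: unresolved FLU-v subjects as cases, unresolved placebo subjects as non-cases. Keep complete-case as a sensitivity analysis.
4. **SAP 5.7.3.** Use the same whole-count rule for the imputed sensitivity analyses.

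The cost is slightly more SAP text and modest programming. If no MMID outcome is missing, the primary result is the same as under the present plan.
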